The study will be a prospective randomized controlled trial, to investigate if administration of EPO and supplemental iron make a clinically significant difference in the number of transfusions given and the morbidity associated with it in infants with cyanotic heart disease. There will be 2 arms in the study, a treatment arm (EPO) and an observational control arm. The patients will be enrolled in the neonatal period after diagnosis and initial palliative procedure (surgical shunt, hybrid procedure, stent in patent ductus arteriosus or right ventricular outflow tract to ensure adequate pulmonary blood flow). They will be followed for 14 weeks from their enrollment. Clinical data will be obtained as appropriate to study the primary and secondary outcomes. The data will be analyzed with a biostatistician to reveal any statistically significant differences between the 2 arms of the study.

E2 Subject Selection and Withdrawal

2.a Inclusion Criteria

- Newborns less than 4 weeks old at diagnosis
- Gestational age ≥ 34 weeks
- Birth weight 2.2-4kg
- Infants with cyanotic heart disease who have had a surgical aorto-pulmonary shunt, hybrid procedure (pulmonary artery bands with a patent ductus arteriosus stent or PGE-1 to maintain ductal patency) or a catheterization intervention that is equivalent to a shunt (patent ductus arteriosus stent, right ventricular outflow tract stent).
- Baseline hematocrit to be below $<40\%$.
- Completes at least 1 injection in the study by 8 weeks of age.

2.a Exclusion Criteria

- Infants diagnosed at greater than 4 weeks of age
- Gestation <34 weeks
- Birth weight <2.2 kg or >4 kg
- Hematocrit $>40\%$
- Newborns with acyanotic heart disease
- Infants with significant co-morbidities
 - Renal failure (Creatinine > 2 standard deviations above age adjusted norm)
 - Hepatic failure (elevated AST/ALT levels > 2 standard deviations above age adjusted norm)
 - Hemolytic disease
 - Hemoglobinopathies (Sickle-cell disease, Thalassemias)

2.b Ethical Considerations

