Informed consent will be obtained by one of the research study members after the initial surgical or catheterization procedure. Each member is well informed of the study objectives, procedures, risks, benefits, physiology of the disease process and mechanism of how the treatment works. The informed consent will be obtained from the patient's parent in a private setting. Details of the study will be presented, and ample time will be given to answer any questions. The parent will have until the eligibility period expires based on the exclusion criteria outlined above to be included in the study. Consent will be obtained in the primary language of the parent. English and Spanish versions of the consent documents will be available and official translators will be used as appropriate. An appropriate official translator will be used during the entire duration of the participant in the study. Informed consent and HIPPA authorization will be documented with the study forms that have been drafted and approved for use in the study and will be kept in a master research file for the duration of the study in a secure area, in a locked drawer by the study team. It will be made clear to the parents that participation in the study is voluntary and that decision to be included or excluded will not compromise the standard of care that the patient deserves. Patients who meet all inclusion criteria except the hematocrit of <40% will be approached and consented, but will not be formally enrolled and randomized into a study group (control or EPO) unless their hematocrit reaches <40% during their eligibility period.

2.d Randomization Method

Study subjects will be randomized 1 to 1 by an algorithm determined by the biostatistician involved. After a study subject has been enrolled into the study, a 2-digit number (1-60) will be assigned. Based on the subject number and predetermined randomization provided, a research pharmacist will dispense the study drug if the subject is enrolled in the intervention arm. This study will not be blinded.

2.e Risks and Benefits

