There is low risk to the patient in regards to side effects of erythropoietin. In general, neonatal population studies have not shown to have significant serious side effects. Blood counts will have to be monitored to observe for polycythemia as this would increase the risk for blood viscosity and thrombosis. There are rare instances in the adult literature with development of Pure Red Cell Aplasia, which is not evident in the neonates. There is some discomfort with the injections, however this is of minimal risk. Lab draws will be done as part of a routine basis. The benefits to receiving this medication are that it may decrease the need of transfusions and hospitalizations in the period prior to a more definitive surgery.

2.f Early Withdrawal of Subjects

As this is a voluntary research study, study subjects will be allowed to withdraw from the study before completion at any time. If a withdrawal occurs before initiation of the intervention, the subject will be excluded from the study.

2.g When and How to Withdraw Subjects

A family may wish to withdraw the study subject from the study at any time. When the decision to withdraw is made after discussions with the clinical staff, a member of the research team will be notified. The date, time, and reason of the withdrawal should be noted by the research member and entered into the database. Families will be approached for permission to follow the course of the patient through the proposed study period even if the intervention was stopped.

2.h Data Collection and Follow-up for Withdrawn Subjects

Families will be approached for permission to follow the course of the patient through the proposed study period even if the intervention was stopped. An intention to treat analysis will be applied to the study subject pertaining to the research arm assigned.

2.i Blood transfusion guidelines

Absolute indications:

- Hematocrit <30%

Relative Indications:

- Hematocrit <40% AND one of the following
 - Clinical acidosis
 - Low oxygen saturations (<75%) in room air
 - Requires supplemental oxygen
 - Requires respiratory support (Ventilator, positive pressure)

When a transfusion is needed, a 10 ml/kg aliquot volume should be given.

E3 Study Drug

3.a Description

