Epoetin alfa is a recombinant form of human erythropoietin used to stimulate erythropoiesis. Iron then helps support proper heme formation with the production of hemoglobin. EPO is administered by injections. Iron will be administered orally or intravenously if orals are not tolerated.

3.b Treatment Regimen

Experimental: Epoetin alfa and iron supplements:

Patients in the treatment group will receive weekly erythropoietin injections for 6 weeks starting before 8 weeks of age (at least one week after their surgery) at 500 units/kg/injection (SQ or IV).(Donato 2005 & Maier 2002) Oral ferrous sulfate 3 mg/kg/day of elemental iron will be given throughout the study if enteral feeds are tolerated which is an accepted treatment for anemia and prevention of anemia. If oral iron cannot be tolerated and there is laboratory evidence of iron deficiency, intravenous iron (either Iron sucrose or Iron dextran) will be used to replace iron stores based on the calculated iron deficit: Total replacement dose (mg of iron) = 0.6 x weight (kg) x [100 -

(actual Hgb /Desired Hgb x 100)]. This will be given in 5-7 mg/kg every day until the total replacement dose is achieved.

Iron studies (Serum iron, ferritin, total iron binding capacity) will be obtained at baseline and at week 14 with the final lab draw. If intravenous iron is used for replacement, iron studies will be repeated after replacement to ensure adequate iron stores.

All injections will be administered by a member of the subject's care team (bedside nurse, nurse practitioner, or physician) with a weekly visit in the cardiology clinic or in the hospital if the infant remains hospitalized after being dispensed by the research pharmacist.

A complete blood count will be obtained in the hospital prior to initiation of treatment for baseline measurements and to confirm eligibility if not obtained within 48 hours prior to the 1st injection as a part of the patient's standard of care. It will be repeated weekly (weeks 2-7) whether inpatient or outpatient, to confirm that there is no over-shoot with a hematocrit >45%. Labs will be reviewed prior to treatment. Treatment will be held for hematocrit levels >45%. There will be another lab drawn 14 weeks after the initial injection. Outpatient visits and lab draws will be paid for by the study grant. All labs will be analyzed by the Rady Children's Hospital Laboratory. The study drug will be provided by the study grant.

Observational Control:

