An observational group will be used as a control. Thus to keep the integrity of the study with minimal bias, strict adherence to the blood transfusion guidelines as listed above is required.

Patients in the control group will have no injections given. This group will receive oral ferrous sulfate 3 mg/kg/day of elemental iron for 6 weeks starting before 8 weeks of age (at least one week after their surgery).

If oral iron cannot be tolerated and there is laboratory evidence of iron deficiency, intravenous iron (either Iron sucrose or iron dextran) will be used to replace iron stores based on the calculated iron deficit: Total replacement dose (mg of iron) = 0.6 x weight (kg) x [100 - (actual Hgb /Desired Hgb x 100)]. This will be given in 5-7 mg/kg every day until the total replacement dose is achieved.

Iron studies (Serum iron, ferritin, total iron binding capacity) will be obtained at baseline and at week 14 with the final lab draw. If intravenous iron is used for replacement, iron studies will be repeated after replacement to ensure adequate iron stores.

A complete blood count will be obtained in the hospital prior to initiation of treatment for baseline measurements and to confirm eligibility if not obtained within 48 hours prior to enrollment as a part of the patient's standard of care. A repeat CBC will be obtained at week 7 and 14 of the subject's participation in the study which will be provided by the study grant. A CBC may be obtained earlier if indicated by the subject's care team as a

part of standard of care. All labs will be analyzed by the Rady Children's Hospital Laboratory.

3.c Method for Assigning Subjects to Treatment Groups

After a study subject has been enrolled, a 2-digit number will be assigned. Based on the number and a pre-randomized allocation scheme devised by the biostatistics department, the subject will be placed into the treatment arm or the control arm of the study.

3.d Preparation and Administration of Study Drug

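### The inclusion bullet requiring a completed study injection cannot be judged before allocation or met by a control, and 2.f, not limited to infants not yet randomised, can remove infants whom 2.h and G3 keep

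*Combined protocol and SAP*

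**What the plan says.** **Eligibility.** E2 2.a includes the bullet "Completes at least 1 injection in the study by 8 weeks of age". Under 2.c, "Patients who meet all inclusion criteria except the hematocrit of <40% will be approached and consented, but will not be formally enrolled and randomized" until the hematocrit falls below the threshold, so hematocrit is the only criterion allowed to be outstanding before randomisation.

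**Order of events.** In 2.d a number is assigned after enrolment and then "a research pharmacist will dispense the study drug if the subject is enrolled in the intervention arm". The study is unblinded. F3 places the first dose after eligibility is confirmed, and only in the EPO arm. For controls, E3 3.b states "Patients in the control group will have no injections given".

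**Withdrawal and analysis set.** 2.f states: "If a withdrawal occurs before initiation of the intervention, the subject will be excluded from the study". For withdrawn subjects, 2.h states: "An intention to treat analysis will be applied to the study subject pertaining to the research arm assigned". G3 analyses all subjects by assigned group whatever they received, and leaves an undosed EPO infant out of the safety analysis only. G5 counts a missing outcome as a transfusion.

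**Follow-up window.** C1 and G4 run it from baseline to 14 weeks after the first injection. E3 3.b says of the EPO arm "There will be another lab drawn 14 weeks after the initial injection", and times the control draws by weeks of participation. E1 says "They will be followed for 14 weeks from their enrollment".

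**The concern.** An inclusion criterion should be a fact known before allocation and defined in the same way in both arms. This one is an event after allocation, and it can occur in one arm only. 2.f raises a similar problem: it sets who counts as a subject by whether the intervention has started, not by whether the infant has been randomised.

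G3 governs how subjects are analysed, while the bullet and 2.f govern who is a subject. If either were applied after randomisation, an infant could leave before G3 takes effect. Allocation is open, so who leaves before the first dose may depend on the arm or on prognosis, and randomisation no longer protects that comparison. The same EPO infant, randomised and withdrawn undosed with no outcome data, is a transfused case under G3 and G5 and absent under 2.f.

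**Working it through.** **1. Can the bullet be judged at enrolment?** The sequence is: consent; hematocrit below the threshold; enrolment and number; allocation; dispensing to the EPO arm; first injection at Visit 1 (2.c, 2.d, 3.c, F3). The event in the bullet is the last step. Controls never reach it. The empty syringe mentioned in 3.d does not change this, because it delivers nothing and Table 2 has no injection row. Read literally with 2.c, nobody could be randomised.

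**2. Does 2.f reach randomised infants?** 2.c creates a group who are consented but not randomised, and excluding those who withdraw is unobjectionable. 2.f does not name that group. A randomised EPO infant withdrawn before the first dose also fits its words, and 2.h and G3 then give the opposite instruction.

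**3. The plan's own sample size.** Inputs from G1 and G4: 80% against 40% transfused, alpha 0.05 (taken as two-sided), power 80%, 1:1. With unpooled variance:

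n = (0.8×0.2 + 0.4×0.6)(1.960 + 0.842)² / 0.40² = 19.6, so 20 per arm, as stated.

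Power at 20 per arm is 80.7% unpooled and 75.2% with the pooled-variance formula.

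**4. What one infant can do.** Illustrative data, not from the documents: 16/20 control and 10/20 EPO transfused, pooled two-proportion z test, z = difference / √[p̄(1−p̄)(1/n₁+1/n₂)].

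| EPO arm analysed | p̄ | z | p |
|---|---|---|---|
| 10/20, all randomised | 26/40 = 0.650 | 0.300/0.1508 = 1.99 | 0.047 |
| 9/19, one transfused infant removed | 25/39 = 0.641 | 0.326/0.1537 = 2.12 | 0.034 |
| 10/19, one untransfused infant removed | 26/39 = 0.667 | 0.274/0.1510 = 1.81 | 0.070 |

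**5. Direction under no true effect.** Take 16/20 transfused in each arm and remove k EPO infants. If all k were transfused, the EPO rate becomes (16−k)/(20−k): 78.9% for k = 1 and 77.8% for k = 2. If none were, it becomes 16/(20−k): 84.2% and 88.9%. If they carry average risk, it stays at 80%.

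**6. Power cost of keeping never-dosed infants.** The documents give no rate, so k = 1 or 2 of 20 is assumed. Kept: EPO rate = [(20−k)×0.4 + k×q]/20 with 20 per arm, where q is the risk in never-dosed infants. Excluded: EPO rate 0.4 with 20−k against 20. Each cell shows unpooled / pooled power.

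| k | Excluded | Kept, q = 0.8 | Kept, counted as transfused (q = 1) |
|---|---|---|---|
| 1 | 79.5 / 74.1% | 76.3 / 70.8% | 73.9 / 68.5% |
| 2 | 78.2 / 73.0% | 71.4 / 66.1% | 66.3 / 61.2% |

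The loss is about 3 or 7 points at 80% risk, and about 6 or 12 points if G5 counts them as transfused. At 30 per arm (the planned maximum of 60), with 2 such infants counted as transfused, power is 87.1% unpooled and 83.7% pooled.

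**The case against.** The best defence is that the literal reading cannot be what was meant. A 1:1 trial with an uninjected control arm cannot require an injection of everyone. 2.c assumes that infants can meet every criterion but hematocrit before randomisation, which makes sense only if the bullet is an age window. E3 3.b gives both arms the same 8-week start. This stands as an account of intent, but the bullet still says something else and needs rewording.

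On 2.f, the natural referent is the consented, unrandomised group, and 2.g and 2.h follow at once with continued follow-up and intention to treat. That is also a fair reading. The text does not limit itself to it, however, and nothing says that G3 takes precedence.

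Few infants are likely to be affected: the EPO-arm baseline review falls within 48 hours of the first injection (Table 1), and that dose is given at an in-hospital visit (F3). This stands, and it limits the weight of the point.

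A reader might infer that the trial will drop undosed EPO infants and so favour EPO. The documents do not support that. No section says the bullet is applied after randomisation, G3 restricts the treated-only rule to safety, and step 5 shows that the shift can be zero or go either way. A reader might also infer that controls have no start for counting transfusions. They do: C1 and G4 start the window at baseline, and F2 and Table 2 give controls a baseline. Only the end of the window lacks a referent for them.

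**Conclusion.** The point holds as two wording faults and one minor inconsistency.

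- The injection bullet cannot serve as an eligibility criterion, whatever was intended. This follows from the sequence in the protocol and needs no assumption.
- 2.f, followed as written, conflicts with 2.h and G3 for any randomised infant who withdraws before the intervention begins, and with G5 if that infant's outcome is missing.
- The end of the counting window is tied to an injection that controls never receive.

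The documents give neither the number of infants affected nor the direction of any bias. The p-values and power losses are illustrations resting on assumed counts, the 80% and 40% rates in G1, and a two-sided test. They show that one infant can matter at 20 per arm, not that the result will be biased. This should be fixed, but it does not undermine the design.

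**What to change.** 1. Replace the bullet with a condition that can be assessed at randomisation in both arms. The sponsor should choose it and reconcile it with the 8-week start wording in E3 3.b and F3, which itself describes an event after allocation.
2. Limit 2.f to withdrawal before randomisation. Every randomised infant then stays in the primary analysis as G3 already states, and G5 already covers missing outcomes, so neither needs a new rule.
3. Give the counting window an end that exists in both arms. Reconcile C1 and G4 with E1 (from enrolment), E3 3.b (weeks of participation for controls) and the Table 2 baseline heading, which refers to a first injection.

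The cost is protocol wording, plus the power loss in step 6. That loss is measured against excluding never-dosed infants, which would be a different comparison and not an intention-to-treat one. Recruiting towards the planned maximum of 60 would offset it.

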Screening for eligibility will be done on the Acute Cardiac Unit at Rady Children's Hospital. When an infant with cyanotic congenital heart disease is identified, the patient will be screened for eligibility based on the inclusion and exclusion criteria described above.

F2 Schedule of Measurements

The schedule of measurements is listed in Table 1 and Table 2. For the treatment arm, a physical exam with oxygen saturation will be recorded weekly from baseline and weeks 1-7, 14. A complete blood count will be drawn at baseline (if not already obtained for clinical use, one week post procedure and ≤ 48 hours prior to 1st injection), weekly from weeks 2-7, and at week 14. Iron studies will be drawn at baseline and week 14 unless indicated in between. All labs will be analyzed by the Rady Children's Hospital Clinical Laboratory whether inpatient or outpatient.

The control arm will have a physical exam with oxygen saturations at baseline, week 7 and 14. A complete blood count will be drawn at baseline (if not already obtained for clinical use, one week post procedure and ≤ 48 hours prior enrollment) week 7 and week 14. Iron studies will be drawn at baseline and week 14 unless indicated in between. All labs will be analyzed by the Rady Children's Hospital Clinical Laboratory whether inpatient or outpatient.

F3 Visit 1

Visit 1 will be prior to 8 weeks of age and at least 1 week post procedure while in the hospital. After confirmation of eligibility for the study, a physical exam and oxygen saturation will be obtained, and the 1st dose of the intervention will be given by the subject's care team if in the EPO arm.

F4 Visit 2 etc.

Visit 2-14 may either be obtained in the hospital or in the clinic setting. A physical exam and oxygen saturation will be obtained. A complete blood count will be obtained weekly from weeks 2-7 in the EPO arm. A complete blood count will be obtained in the control group at week 7 or earlier if indicated by the subject's care team. Study injections will be given after the lab has been reviewed and confirmed there is no overshoot (Hct >45%). There will be a final physical exam and labs at week 14 of the study, which will complete the participation of the study.

F5 Safety and Adverse Events

5.a Safety and Compliance Monitoring

Safety and Compliance Monitoring will follow standard principles as outlined below.

5.b Medical Monitoring

i Investigator

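### The blood count that confirms eligibility is tied to the first injection in the EPO arm and to enrolment in controls, so an entry criterion can be applied after open allocation, mainly in one arm

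*Combined protocol and SAP*

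**What the plan says.** Section E2 2.c sets a hematocrit condition before randomisation for everyone: an infant "will not be formally enrolled and randomized into a study group (control or EPO) unless their hematocrit reaches <40% during their eligibility period". It gives no limit on the age of that count. Sections E2 2.d and E3 3.c assign the study number, and with it the arm, after enrolment. The study is not blinded.

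E3 3.b then describes a count that serves both as baseline and as an eligibility check. In the EPO arm it is drawn "to confirm eligibility if not obtained within 48 hours prior to the 1st injection"; in the control arm, "to confirm eligibility if not obtained within 48 hours prior to enrollment as a part of the patient's standard of care". F2 repeats the two anchors: "one week post procedure and ≤ 48 hours prior to 1st injection), weekly from weeks 2-7, and at week 14" for EPO and "one week post procedure and ≤ 48 hours prior enrollment) week 7 and week 14" for controls. The Table 1 baseline heading agrees with the EPO text. Table 2, the control schedule, carries the same injection-based heading, which contradicts 3.b and F2.

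F3 (Visit 1) reads "After confirmation of eligibility for the study, a physical exam and oxygen saturation will be obtained" and then has the first dose given in the EPO arm. The inclusion criteria in E2 2.a test the baseline hematocrit against 40% and also require at least one study injection by 8 weeks of age. Section 2.f excludes a subject who withdraws before the intervention begins. G3 analyses every subject in the assigned group whatever treatment was received.

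**The concern.** Eligibility should be settled before the arm is known. Here the anchor for one arm is an event that exists only once the infant has been allocated to that arm. An entry criterion tested at that point is tested with the arm known, and on a schedule that the other arm does not share.

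If infants left the trial or the analysis on that test, the two groups would no longer be the groups that were randomised. Those affected would be selected on hematocrit, the variable that drives the transfusion indications in 2.i and so the primary outcome. The baseline values would also be taken at different times relative to randomisation. With a minimum of 20 infants per arm, a few such losses would be visible in the result.

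**Working it through.** **1. The rules side by side**

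| Step | EPO arm | Control arm |
|---|---|---|
| Hematocrit condition before randomisation (2.c) | below 40%, no age limit on the count | same |
| Eligibility and baseline count (3.b, F2) | within 48 h before first injection | within 48 h before enrolment, otherwise drawn before treatment starts |
| Baseline heading in the schedule | Table 1: injection-based | Table 2: injection-based, but no injection is given |
| Next scheduled count | week 2 | week 7 |

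**2. When the difference takes effect.** The order is: count, enrolment, allocation, first dose. If the count used for randomisation is still under 48 hours old at the first injection, it serves both purposes and nothing differs. If it is older, the EPO text calls for a new eligibility count after allocation. A control with a count in the 48 hours before enrolment needs none. The first injection must come at least one week after the procedure and before 8 weeks of age (3.b), but no maximum gap from randomisation to first dose is given.

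**3. What could follow from the new count.** If it is the EPO infant's baseline, a value of 40% or more does not meet the baseline hematocrit criterion. If the infant is then not dosed, the one-injection criterion is not met either, and only the EPO arm can meet that criterion at all. Section 2.f would add exclusion if the family withdrew before the intervention began. G3 points the other way and keeps the infant in the EPO group. No section settles which prevails.

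**4. The plan's own figures as the base for an illustration.** Inputs from G1 and G4: 80% of controls and 40% of EPO infants transfused, 20 per arm, α = 0.05 (taken as two-sided), 80% power. With the unpooled formula, n = (1.960 + 0.842)² × (0.8×0.2 + 0.4×0.6) / 0.4² = 19.6, so 20 per arm, with power of 80.7%. This reproduces the stated figure. With the pooled z test, power at 20 per arm is 75.2%: SE₀ = √(0.6×0.4×2/20) = 0.1549, SE₁ = √((0.16 + 0.24)/20) = 0.1414, and Φ((0.4 − 1.960×0.1549)/0.1414) = Φ(0.681).

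**5. Effect of losing k EPO infants and no controls (k is assumed).** Expected EPO transfused: 0.4 × 20 = 8. Power is for the pooled z test.

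| k | Lost infants would not have been transfused | Lost infants had been transfused | Kept, outcome missing, set to transfused (G5); would not have been transfused |
|---|---|---|---|
| 0 | 8/20 = 40.0%, power 75.2% | 8/20 = 40.0%, power 75.2% | 8/20 = 40.0%, power 75.2% |
| 2 | 8/18 = 44.4%, power 62.9% | 6/18 = 33.3%, power 85.7% | 10/20 = 50.0%, power 51.2% |
| 4 | 8/16 = 50.0%, power 47.4% | 4/16 = 25.0%, power 94.4% | 12/20 = 60.0%, power 27.6% |

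**6. How many infants might re-test at 40% or above.** The documents give no data, so every input is an assumption: first hematocrit normal with mean 35 or 37 and SD 3, limited to 28–40; change to the second count with SD 1.5 to 3.5; every infant re-drawn. With no average change, 3.4% to 18.2% re-test at 40% or above. With an average fall of 2 points, 0.3% to about 8%. Of 20 infants this is anything from none to about 4 (0.182 × 20 = 3.6).

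**The case against.** The strongest reply is that nothing in the documents removes a randomised infant on this count. The only stated hematocrit action on treatment is a hold above 45%. G3 analyses subjects as assigned, and 2.h applies intention to treat to withdrawn subjects. This stands: removal is an inference from a count whose stated purpose is to confirm eligibility. The reply does not explain what confirming eligibility after allocation is for, nor how the one-injection criterion fits with G3.

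A reader might also infer that only EPO infants are re-checked. The documents do not support that. The control text allows a count before treatment starts when none was obtained in the 48 hours before enrolment, Table 2 gives controls the injection-based window, and F3 does not limit the eligibility check to EPO. The asymmetry is in the stated rule and is partial.

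Nor is a gap of more than 48 hours established. The Table 1 timing is compatible with enrolment and first dose close together, in which case one count serves both purposes.

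Finally, a reader might infer a bias against EPO of known size, on the view that excluded infants are those least likely to need transfusion. That would hold for a hematocrit that rose by itself. One that rose after a transfusion works the other way, since excluding that infant removes a transfused case from the EPO arm. A downward average change is also plausible, because section A1 says these infants share the normal early fall in red cells, and it would make re-tests at 40% or above less common.

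**Conclusion.** The point holds in a limited form. The eligibility and baseline count has a different anchor in each arm, stated in both 3.b and F2, and Table 2 contradicts both. Because allocation is open and precedes the first injection, the text can place an entry criterion after allocation, mainly in the EPO arm, and the resulting exclusions would conflict with G3.

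This depends on two things the documents leave open: that more than 48 hours sometimes pass between the last count and the first dose, and that someone acts on the new count as an eligibility decision. The size cannot be derived from the documents and the direction is not fixed. The tabulated rates show only that one-sided losses of 2 to 4 infants would matter at 20 per arm; they are not a forecast. The documents do not support saying that the randomised comparison is already broken. They do contain a rule that differs by arm and should be corrected before it has consequences.

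**What to change.** - In both arms, define the eligibility and baseline count as the last one within 48 hours before randomisation.
- State that no count after randomisation changes eligibility or membership of the intention-to-treat set.
- Align 3.b, F2, F3 and the baseline headings of Tables 1 and 2 with that definition, and remove the reference to an injection from the control schedule.
- Reconcile the one-injection inclusion criterion and section 2.f with G3, so that an infant who is randomised but not dosed is analysed in the assigned arm.
- How treatment is handled when a pre-injection hematocrit is no longer below 40% is for the sponsor to reconcile across the sections. That decision should be kept separate from eligibility and from the analysis set.

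The cost is wording in those sections and two table headings. The sample size need not change. Any count the care team wants before the first injection can still be taken as a safety value.
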